3. STUDY DESIGN

[figure not shown]
This study is designed as a randomized, two arm clinical trial to evaluate the efficacy of self-administered hypnosis for the treatment of hot flashes. The primary outcome will be the hot flash score,

which is determined from the frequency and severity of hot flashes obtained using the Hot Flash Daily Diary and will be determined at the 6-week data point.

Secondary endpoints will include: daily activity interference and overall quality of life measured by the Hot Flash Related Daily Interference Scale (HFRDIS), sleep disturbance measured by the Pittsburgh Sleep Quality Index (PSQI), and anxiety assessed by the PROMIS Emotional Distress - Anxiety Scale the Hot Flash Daily Diary at 6 and 12 weeks, and the Subject Global Impression of Change, at 6 weeks only.

It is expected that the hypnosis intervention will lead to decreased sympathetic nervous system (SNS) activity and increased parasympathetic tone. This shift in autonomic balance will have beneficial effects on

Figure 1: Conceptual Framework

hot flash score (frequency and severity-the primary outcome). Improvement in hot flashes will result in improvement in the secondary outcomes (activity interference, quality of life, sleep quality, and anxiety). Additionally, it is expected that perceived stress will decrease in the treatment group due to the intervention, which will correspond to further decrease of the hot flash score, but act as a mediator; and this will be measured with the Perceived Stress Scale. Because both autonomic arousal^[71] and psychological stress^[57] are believed to play a critical role in the initiation of hot flashes, we hypothesize that improvement in primary and secondary outcomes will be mediated by perceived stress and the autonomic response to hypnosis (**Figure 1**).

The comparison condition, called sham white noise hypnosis, is structured to account for non-specific effects of general time and attention, in addition to non-hypnotic audio-recordings to evaluate whether this self-administered hypnosis will reduce hot flashes more than an appropriate control group. This represents a rigorous RCT design.

There will be 232 participants who are postmenopausal or breast cancer survivors and wish to

avoid hormonal therapy to treat hot flashes.

Eligible participants will be randomized to either self-administered hypnosis intervention or selfadministered sham white noise hypnosis which includes listening to white noise. Randomization will be accomplished by the statistical team using stratified permuted block randomization with fixed blocks of size four. Two strata will be used: site (University of Michigan or Baylor University) and participant subgroup (post-menopausal or breast cancer). All randomization block permutations will be generated, and one permutation will be randomly assigned to each block. The randomization information will be printed on individual cards, each of which will be placed in a brown security envelope and sealed (one card per envelope). The envelopes will be chronologically numbered and assigned according to that order. It is expected that each site (Baylor University and University of MI) will each recruit approximately half of the participants, but each site will receive two sets of 116 envelopes – one set of 116 for each participant subgroup. It is not expected that there be an equal distribution of participants who are post-menopausal or breast cancer survivors; rather, the randomization strategy ensures an equal distribution of each subgroup into the self-administered hypnosis intervention or self-administered sham white noise hypnosis condition regardless of the proportion of each participant subgroup within site. For example, if Baylor University randomizes 100 participants who are post-menopausal and 16 who are breast cancer survivors, having two sets of 116 randomization envelopes ensures that (1) there are enough envelopes and (2) there are 50 postmenopausal and 8 breast cancer survivors in each condition. Therefore, one set of sealed envelopes for post-menopausal participants with group assignment and one set of sealed envelopes for breast cancer survivors with group assignment will be provided to both [name] team and [name] team. The randomization list will be kept by the statistician and person(s) who will randomize participants, educating them about their treatment assignment, and not accessible to persons who will be educating, obtaining consent from the participants, collecting data, or interacting in any other capacity which involves contact with participants, as this may possibly cause bias in the recruitment process. The unused randomization envelopes will be destroyed.

The accrual and enrollment duration for the entire trial is expected to be approximately 39 months. (**Table 1**) Individual participant time in the study will be approximately 13 weeks (i.e., baseline week through week 12 follow-up).

Eligible participants will be randomly assigned to either the selfadministered hypnosis intervention group or the self-administered sham white noise group. The study hypothesis will be blinded such that all participants will be told there are

Table 1

MONTHS 1-9 Training; preparation; recruitment	MONTHS 10-42 Recruitment; sessions; data collection; data entry	MONTHS 43-47 Complete Data Collection	MONTHS 48-60 Data Management; Analyses; Write- ups
Train staff, research coordinator, and research contact staff	Recruit participants	Complete study visits	Finalize data cleaning
Develop and assemble study materials, record all audio recordings	Format data files, prepare data sets, enter data	Collect Follow- Up data and complete data entry	Analyze data
Regulatory procedures to begin recruitment		Begin planning manuscripts and presentations	Prepare manuscripts and present papers/posters

two different self-administered hypnosis programs being evaluated. Both groups will meet with a research contact staff two times (consent/baseline visit and randomization/education visit) in person (or by telephone or video conference during COVID-19 restrictions) and further contact will be by phone, with approximately 10-day intervals between calls for a total five phone calls over a 6-week span (**Table 2**). One final phone call will occur at week 11 to remind participants about the 12 week data collection. The baseline appointment will include completion of all baseline questionnaires (HFRDIS, PSQI, PROMIS Emotional Distress-Anxiety, and PSS). Participants will also be provided with a hot flash daily diary (for 7 days of baseline data collection), saliva collection materials, and a

Table 2: Weekly participant contact

Baseline In- person (or telephone or video	During the week of Week 1 Call 1	Call 2	Call 3	Call 4	Call 5
conference during COVID- 19 restrictions) Research Staff Interaction followed by 7- day Hot Flash Daily Diary; then Randomization/ education visit	Research Staff Phone contact	Research Staff Phone contact	Research Staff Phone contact	Research Staff Phone contact	Research Staff Phone contact

Polar V800 HRV device (each for two days of baseline sample/data collection) prior to using the recordings. The intent of the baseline visit is to establish rapport with the participant and to ensure understanding of the baseline data collection related to the saliva, heart rate and hot flash diary. Within 30 days of the baseline data collection, the participants will be scheduled for a randomization visit where they will learn in detail about implementing their assigned intervention. Participants in the hypnosis group will also receive the hypnotizability assessment at the randomization visit. The study phone visits are not therapeutic for hot flashes. The phone calls will maintain contact to encourage practice of the self-administered programs and answer study related questions. In addition, administrative phone calls will occur as needed to assure data collection has been sent and received, as well as to answer questions relating to participation in the study. Participants in the self-administered hypnosis group will also receive the hypnotizability assessment ([name] Hypnotizability Scale [EHS] which is also not a therapeutic intervention. The EHS-CF will be administered if visit is by telephone or video conference (during COVID-19 restrictions).

Audio recordings will be developed and distributed to the participants based on individual randomization. The recordings will be available to the participants as pre-recorded digital audio files, flash drive, or CDs and be given during the randomization visit. The audio recordings will be mailed to the participant if the randomization visit will occur through phone or video conference due to COVID-19 restrictions or participants will be provided with digital audio files. For participants who prefer a flash drive or CDs, those will be provided. Additionally, if a participant prefers to use CDs, but does not have a CD player, one will be provided. Based on their past research experience, [name] will facilitate this process in that, through years of clinical practice and research, it has been found that when women are asked about a place that is safe, positive and relaxing for them, only a few "scenes" of imagery come up: beach, lake, forest, and mountains. [69]

Therefore, as illustrated in **Table 3**, the recordings for the Self-Hypnosis Intervention Program will be created using preferred imagery for the inductions provided for Weeks 1 and 2. For Week 3, a hypnosis

induction will be included which will instruct and allow for participants to individualize and focus on a personal imagery that prompt feelings of coolness and comfort. This type of induction addresses the

Table 3	Table 3: Audio-recording contents					
Week	Self-Hypnosis Intervention	Sham White Noise Hypnosis Control				
1	Hypnotic Induction with imagery 1	White Noise				
2	Hypnotic Induction with imagery 2	White Noise				
3	Hypnotic Induction Individualization	White Noise				
4	Hypnotic Induction Self-Hypnosis	White Noise				
5	Hypnotic Induction Integration	White Noise				
6	Preferred recording(s) from Weeks 1-5	White Noise				

needs of women who would respond better to a less specific suggestion. The Week 4 recording will provide instruction in self-hypnosis without the use of the recordings. Week 5 will guide the participant as they move to integrate the intervention into their daily lives using both methods (recorded and non-recorded self-hypnosis practice); and participants will be encouraged to use the recording of their choice during the final week (Week 6) of the program.

The self-administered sham white noise hypnosis recordings will be one recording of white noise, which will time-match the audio recordings designed for the self-hypnosis intervention program. Participants in the self-administered sham white noise hypnosis group will use the hot flash education recording week 1 and the white noise recording weeks 2-6.

Each participant will receive a toolkit in one well organized binder that includes specific instructions for each week, tailored to the treatment assignment, instructions about the saliva collection and HRV measurement, the hot flash diaries, practice logs, and questionnaires for weeks 6 and 12. The toolkit will also include sufficient addressed, stamped envelopes for questionnaire and saliva and HRV return.

4. SELECTION AND ENROLLMENT OF PARTICIPANTS

4.1 Inclusion Criteria

Participants must meet all inclusion criteria to participate in this study.
Postmenopausal as defined by one of the following criteria:

- 1) no menstrual period in the past 12 months
- 2) chemical menopause (LHRH antagonists)
- 3) surgical menopause (bilateral oophorectomy)
- 4) evidence of menopause status per FSH and estradiol levels per institutional guidelines.
- Self-reported history of a minimum of 4 hot flashes per day or 28 hot flashes per week at baseline
- Age over 18 years and able to give consent for participation in the study
- Participants on antidepressants for hot flashes are allowed on study if the antidepressant has been for at least 2 months, there are no plans to change the dose or antidepressant, and the number of hot flashes meets the eligibility criteria of at least 4 hot flashes per day or 28 per week.
- Have discontinued other putative therapies for hot flashes for at least one month prior to enrollment (Vitamin E will be allowed)
- Women with a diagnosis of DCIS or invasive breast cancer stages 0-III are allowed to participate and may be on endocrine therapy of any kind. If on endocrine therapy, women must be on endocrine therapy for 4 weeks and not expected to stop endocrine therapy during the study. If not on endocrine therapy, participants should not be planning to start during the course of the study. However, unexpected treatment with endocrine therapy will not require study withdrawal but will be recorded and considered in the analysis.

4.2 Exclusion Criteria

All candidates meeting any of the exclusion criteria at baseline will be excluded from study participation.

- Receiving other simultaneous treatment for hot flashes except antidepressants.
- Diagnosis of Major Depressive disorder or acute anxiety disorder in the past 5 years.
- Using any Complementary and Alternative Medicine (CAM) treatments for vasomotor symptoms. (This would include soy products and other phytoestrogens, black cohosh, and any mind-body techniques including meditation, yoga, etc.). If any therapies are used for reasons other than hot flashes and hot flash frequency if woman meets inclusion criteria, then woman is eligible)
- Stage IV breast cancer
- Serious psychological illness, specifically psychoses, schizophrenia or borderline personality disorder
- Currently using hypnosis for any reason
- PHQ-4 score ≥ 9
- Non-English speaking

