6. STUDY PROCEDURES

Schedule of Activities 6.1

Table 4: Schedule of Activities	Enrollmen	BL wk	Treatment and Follow-up in weeks						
	1 2 3		3	3 4 5		6 12			
Screening Checklist including PHQ-4	Х								
Informed Consent	X								
Demographic Questionnaire & Health History Intake		Х							
Aim 1 (primary outcome)									
Hot flash daily diary		D	D	D	D	D	D	D	D
Aim 2 (secondary outcomes)									
Hot Flash Related Daily Interference Scale		Х						Х	Х
PROMIS Emotional Distress- Anxiety Scale		Х						Х	Х
Pittsburgh Sleep Quality Index		Х						Х	Х
Global Impression of change								Х	
Aim 3 (mediators and moderators)									
Saliva collection for diurnal cortisol*		Х						Х	
HRV through Polar V800**		Х						Х	
[name] Hypnotizability Scale (only hypnosis group)		X***							
Frequency of home practice			D	D	D	D	D	D	D
Check In Phone Calls			Х	Х	Х	Х	Х	†	1

6.2 **Description of Evaluations**

The Schedule of Measures (**Table 4**) defines what is to be done at each week of the study period, which is approximately 13 weeks.

It is divided primarily by the type of evaluation (i.e.; Enrollment, Baseline, and Treatment & Follow-up). The Treatment & Follow-up period is further divided by study weeks.

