6.2.1.2 Screening

Screening is to identify eligible participants and will be completed during the completion

of the Inclusion/Exclusion Criteria Screening Checklist, after which individuals may be scheduled at any time to begin study participation, with the following exception:

• If at screening, the individual self-reports the use of other putative therapies for hot flashes for at least one month prior to enrollment, then a washout period of one month will be required prior to the scheduling of the baseline appointment.

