6.2.2.3 Randomization

Randomization will be assigned after baseline measures have been completed and prior to intervention instruction and administration.

If a period of more than 30 days passes after the screen is complete without the individual coming to the lab for the baseline appointment (except in the case of washout of putative therapies for hot flashes for one month prior to enrollment on study), the initial verbal consent will be considered void, and will need to be repeated and another Inclusion/Exclusion Criteria Screen Checklist will be completed prior to rescheduling the baseline visit. Since randomization will not have taken place, this will not impact accrual numbers but will be counted as a screen failure. Participants who attend the baseline visit and sign the consent form but then never return for their randomization visit will also be considered screen failures, but these women will be replaced to maintain statistical power.

Once randomization has been completed, efforts will be made to ensure that participants enrolled are assisted and encouraged to initiate and complete participation in the materials associated with the condition to which they are assigned.

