7.1 Specification of Safety Parameters

We are excluding women around mental health diagnoses and screening with the PHQ-4 that would make hypnosis a potentially unsafe intervention.

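### The PHQ-4 safety screen is scheduled once, with the screening checklist, and is not repeated before allocation, so at the permitted limit the score is about two months old at randomization

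*Combined protocol and SAP*

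**What the plan says.** - **When the exclusion applies.** Section 4.2 opens: "All candidates meeting any of the exclusion criteria at baseline will be excluded from study participation". The list includes a PHQ-4 score of 9 or more, alongside recent diagnoses of major depressive or acute anxiety disorder and serious psychological illness.
- **What the PHQ-4 is for.** Section 7.1: "We are excluding women around mental health diagnoses and screening with the PHQ-4 that would make hypnosis a potentially unsafe intervention".
- **When it is given.** In Table 4 the row "Screening Checklist including PHQ-4" has a single mark, in the enrollment column. Section 6.2.1 allows the checklist to be done by phone, and Section 4.3 describes a phone screening appointment. The baseline battery in Section 6.2.2.2 does not list the PHQ-4.
- **When the screen expires.** Section 6.2.2.3: "If a period of more than 30 days passes after the screen is complete" with no baseline visit, "the initial verbal consent will be considered void, and will need to be repeated and another Inclusion/Exclusion Criteria Screen Checklist will be completed". One group is carved out: "except in the case of washout of putative therapies for hot flashes for one month prior to enrollment on study".
- **Washout.** For a woman who reports a hot flash therapy at screening, Section 6.2.1.2 says: "then a washout period of one month will be required prior to the scheduling of the baseline appointment".
- **Baseline to randomization.** Sections 3 and 10.1 place the randomization visit within 30 days of the baseline data collection, and the baseline diary covers the 7 days after the baseline visit. For remote visits, Section 4.3 puts allocation several days ahead of the visit.
- **Losses before randomization.** Section 6.2.2.3 counts women who consent but do not return for randomization as screen failures and adds that "these women will be replaced to maintain statistical power".

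**The concern.** The two layers in Section 7.1 age differently. A five-year diagnosis history changes little over a couple of months. A symptom score can change, and it is the only layer that picks up current, undiagnosed depression or anxiety. The plan accepts that a screen goes stale, because it voids one that is more than 30 days old when the baseline visit has not taken place. That protection ends at the baseline visit, does not run on to allocation, and does not cover women in washout.

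A woman who scored below 9 on the phone and has since risen to 9 or more could therefore be allocated to hypnosis on the older score. At stake is the currency of one safety screen.

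**Working it through.** The plan states no figure for the age of the PHQ-4 score at randomization, so there is nothing to reproduce. The age follows from adding the stated windows.

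**Inputs**
- d = days from screen to baseline visit. Routine participant: 0 to 30 without a re-screen (Section 6.2.2.3). Washout participant: no explicit upper limit.
- Baseline data collection: 7 days after the baseline visit (Section 10.1).
- g = days from baseline visit to randomization visit. At least 7. At most 30 if the 30-day window in Sections 3 and 10.1 runs from the baseline visit, or 7 + 30 = 37 if it runs from the end of the baseline week.
- One month is taken as 30 days (an assumption).

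**Formula.** Age of score at the randomization visit = d + g.

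**Routine participant**
- Minimum: 0 + 7 = 7 days.
- Randomized as soon as the baseline week ends: d + 7, so 7 to 37 days.
- Permitted maximum: 30 + 30 = 60 days, or 30 + 37 = 67 days.

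**Washout participant**
- Washout month starts on the day of the screen and randomization follows the baseline week at once: 30 + 7 = 37 days. This is the lowest value under that assumption.
- Same start, baseline visit on the day washout ends, full second window: 30 + 30 = 60 or 30 + 37 = 67 days.
- If a further 30 days to the baseline visit were allowed after washout: 60 + 30 = 90 or 60 + 37 = 97 days. The text neither grants nor forbids this.
- Therapy already stopped 14 days before the screen, with that time credited toward the one month required by Section 4.1: (30 − 14) + 7 = 23 days at the earliest.

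**With the PHQ-4 repeated at the baseline visit.** Age = g, so the maximum is 30 or 37 days for every woman, whether or not she came through washout.

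For remote visits allocation precedes the visit by several days, so the score is slightly younger at allocation than these sums show.

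**Is anything else a substitute before allocation?**
- The health history intake evaluates severe or acute anxiety or agitation (Section 7.2). No cut-off is stated and depression is not mentioned.
- PROMIS Anxiety and the Perceived Stress Scale are collected at baseline. Neither has an exclusion threshold and neither screens for depression.
- Section 6.2.1 describes the PHQ-4 as covering both depression and anxiety. Nothing in the baseline battery repeats it.

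**The case against.** The strongest reply is that Section 4.3 says how Section 4.2 is put into practice: eligibility is determined from the checklist, which carries the 4.1 and 4.2 criteria. On that reading the words about baseline in 4.2 simply mean study entry, much as 4.1 uses them for a self-reported hot flash history. This is plausible. A reader might infer that the protocol contradicts itself, or that women are being randomized in breach of 4.2. The documents do not go that far. What stands is that a safety criterion is measured once and not refreshed before allocation.

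Three further objections hold in part.
- **The maximum is not the plan.** Section 3 puts participation at about 13 weeks, one baseline week plus 12, which leaves almost no planned gap after baseline. The 30-day wording may also limit only when the visit is scheduled, so 60 to 67 days is not a firm bound. A reader might also conclude that the score may reach twice the plan's own limit. That comparison fails, because the 30-day rule covers screen to baseline visit, not screen to randomization.
- **Washout varies.** A reader might infer that every washout woman has a score more than 30 days old. That needs the washout to start at the screen; the 23-day case above shows otherwise. The exemption can also be read as covering only the washout month.
- **Other safeguards exist.** Staff collect current distress data at baseline, the diagnosis exclusions apply throughout, and after randomization there is escalation of distress by research assistants (Section 7.2) and CTCAE grading at each call (Section 7.3). These reduce the consequence. The baseline measures have no cut-off, and the monitoring starts only after allocation.

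Finally, the checklist, the intake form and the Manual of Procedures are not among the documents, and any of them might contain a re-check.

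**Conclusion.** The point holds as a low-severity participant-safety improvement. The PHQ-4 is scheduled once and not repeated before allocation. The permitted windows let the score reach about 60 to 67 days at randomization for a routine participant, and washout women have no explicit upper limit. The figures assume a 30-day month, that the 30-day window limits the randomization visit itself, and, for the 37-day washout value, that washout begins at the screen.

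The documents give no rate at which women would move to 9 or more, so the number affected cannot be estimated and none is claimed. Section 7.2 describes the risks as minimal. A reader might suspect an effect on power or on the treatment comparison. Nothing supports that: the sample size, the randomization scheme and the primary analysis do not depend on when the PHQ-4 is taken. No gap in monitoring after randomization is claimed either.

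**What to change.** In Table 4 and Section 6.2.2, add the 4-item PHQ-4 to the baseline visit for all women, including those who came through washout, and apply the cut-off of 9 or more to that score before allocation. A woman at or above it is referred as Section 6.2.1 already provides and counted as a screen failure. For remote participants, ask the items during the baseline call so that the score is in hand before allocation, which there precedes the randomization visit. If the Manual of Procedures already contains such a re-check, it is enough to state it in the protocol.

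The cost is a protocol amendment, one extra mark in Table 4, four questions at an existing contact and one score checked before the envelope is opened. The downside is that a few women become ineligible after consent but before randomization. Section 6.2.2.1 already expects losses at that stage, and the replacement rule for women who do not return for randomization can be extended to them. No on-study PHQ-4 is needed.
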